PROTOCOL

Official title: Randomized and Controlled Prospective Study on Use of the Adhesive Elastic Tape to Control Hand Edema in Patients With a Wrist Fracture Treated With Forearm Plaster

NCT number NCT04683887

Document version 2.0

Document date 15 feb 2022

INTRODUCTION

Wrist fractures are a very common event affecting patients of all ages (Crowe et al., 2020) and are estimated to represent approximately 10-25% of all fractures (Geraci et al., 2011; Smeraglia et al., 2016; Watson et al., 2018). These fractures are treated with closed reduction and forearm circular cast in 70-90% of cases (Letsch et al., 2003). There are several immobilization techniques, although there is no evidence identifying the best one in maintaining reduction. The forearm circular cast seems to be the best tolerated by patients (Okamura et al., 2018; Park et al., 2017; Peivandi et al., 2011).

Wrist fracture patients often develop oedema (Knygsand-Roenhoej & Maribo, 2011) and the presence of plaster increases the risk (Dresing et al., 2017). In 2019, 17.4% of patients with wrist fractures treated with circular plaster cast at one Orthopedic Emergency Room (OER) of Northern Italy, had a second visit in OER for oedema, pain or "intolerance to the plaster cast".

Kase has developed an adhesive elastic tape from 1973 to 1979 and marketed in 1982 with the name Kinesio tape (Wu et al., 2015). Since then, several authors have described this technique (Kase, 2005; Blow, 2015; Kumbrink et al., 2019) and several companies have started producing tapes with analogue characteristics. These devices are thin elastic stripes usually made of cotton, containing longitudinal interwoven elastic fibers and acrylic glue that is spread in a wavelike pattern. The material elasticity is approximately 130–140%, and the amount of traction used in its application to the skin influences the skin itself and various subcutaneous layers (Kase, 2005; Blow, 2015; Kumbrink et al., 2019). Taping technique is used to control the oedema, support of soft tissues, protect the joints and alleviate the heat produced by active inflammation.

There are many studies in the literature that demonstrate the efficacy of adhesive elastic tape in reducing lymphoedema in different pathologic conditions. Oedema secondary to breast cancer treatment is reduced by taping application compared to untreated controls (Lipinska et al., 2007; Pajero Otero et al., 2019; Tantawy et al., 2019). A recent meta-analysis showed a positive effect in reducing lymphoedema (perimeter or volume) before versus after taping treatment, although no significant differences were found comparing taping with control group or other treatments (Kasawara et al., 2018). A meta-analysis concerning limb lymphedema, not necessarily due to

breast cancer, did not detect differences in the volume drained by the tape compared to the control, but found a decrease in symptoms related to oedema (Gatt et al., 2017). A single study appears to support the no-effect thesis (Ergin et al., 2019).

Besides breast cancer, tape application has shown advantages after orthopedic surgery. The application of the tape seems to bring benefit in the post-operative period of knee arthroplasty, whether or not associated with manual lymphatic drainage (Donec & Kriščiūnas, 2014; Tornatore et al., 2020) and in the reduction of oedema in the knee after arthroscopy (Balki et al., 2016; Gülenç et al., 2019) however a trial does not recognize its effect in reducing oedema after shoulder arthroscopy (Gülenç et al., 2019). A systematic review supports the positive effects of the tape on post-operative oedema, although it recognizes some limitations including the small number of trials evaluated (Hörmann et al., 2020). One study reports good results in the control of oedema in patients treated with an Ilizarov type fixator (Białoszewski et al., 2009).

Given the importance of oedema control and the lack of definitive evidence in the literature regarding the effectiveness of the adhesive elastic tape, we decided to perform this study in order to evaluate tape effectiveness in counteracting the oedema formation in the hand of wrist fractured adult patients treated with forearm circular cast.

METHODS

Aim

The primary aim of our study is to evaluate whether the application of the tape with lymphatic technique to the fingers, both dorsal and volar, of wrist fractured patients treated with a forearm circular plaster cast is able to reduce the formation of hand oedema, compared to the untreated controls. Furthermore, we aim to assess the differences in pain and cast tolerability between the intervention group and the control group.

Primary endpoints

(i) difference in the circumference of the thumb between baseline (T0) and 7-days follow-up (T1), and (ii) difference in the circumference of the remaining 4 fingers merged together, between T0 and T1.

Secondary endpoints

(i) pain intensity at T0 and T1, (ii) analgesic use during the previous 4 hours at T0 and T1, and (iii) OER re-entry number for “intolerance to the plaster cast”.

Design

Our study is a randomized controlled superiority trial, with parallel design and blinded data processing, developed at OER of Local Health Unit of Piacenza.

The ID NCT04683887 identify this study on clinicaltrials.gov.

Participant characteristics

The patients' eligibility criteria to participate in our study are described in Table 1.

Sample size calculation

The sample size was calculated using the GPower 3.1 Software, setting the following parameters: effect size: 0.4, error α = 0.05, power = 0.80 and allocation ratio = 1.

The resulting sample size is 100 subjects per arm; the number of patients to be enrolled will be a total of 220 (110 per group), taking into account a 10% loss to follow up. The choice of medium effect size (0.4) was made based on feasibility and available literature (Gülenç et al., 2019; Pajero Otero et al., 2019; Tantawy et al., 2019) despite the absence of similar studies for pathology/type of intervention/primary endpoint.

Setting

Patient enrolment, execution of the fracture reduction maneuver, application of the plaster cast, application of the tape for the investigational treatment patient group, and endpoint T0 measurements will take place at the OER service of Local Health Unit of Piacenza. On day 7 the

tapes will be removed and endpoint T1 measurements will be assessed at the Orthopedics and Traumatology outpatient clinic.

Preliminary procedures and nurses' training

Before the enrolment of the first patient, all OER nurses will be trained for the tape application by a certified instructor.

All OER orthopedic doctors and nurses are trained and skilled in the closed reduction technique and forearm circular cast application. The closed reduction technique, done manually by three operators, and circular cast application are performed as described in Dresing et al. (2017).

Patients' enrolment

After having performed the necessary radiographic investigations and verified the presence of all inclusion criteria and the absence of exclusion criteria, complete oral and written information about the study will be given to each patient by OER nurses and physicians. A reflection period will be guaranteed to the patient during the waiting time before the control X-ray after reduction procedure.

Enrolment will be effective as soon as the patient has signed the consent form. We will then assign him/her to the intervention or control group after a telephone call to the Data Analysis Manager, as described in the following section.

Randomization, blind and control

We will generate the randomization list through the program called "Random Number Generator", available at <https://stattrek.com/statistics/random-number-generator.aspx>. The randomization will be simple with 1:1 allocation. The randomization list, known only to the Data Analysis Manager not involved in the clinical evaluation of patients, will be implemented and hidden inside a specific file protected by a password to prevent identification of the patient. We will assign the enrolled patients to group 0 or 1 according to the list by a telephone contact between Investigators and Data Analysis Manager.

The data-analyzing Researcher will not know which of the two groups will be the intervention nor the control one, to guarantee the blind. The Investigators are not allowed to collect data in a blind way due to the nature of study intervention.

We decided not to apply any type of alternative strip to the control group. Even if positioned without lymphatic technique, the tape would maintain its elastic properties and we cannot exclude that it may still have an effect. The application of a strip with properties different from the tape on one side would still have the adhesive effect induced by the glue-skin interaction, stimulating muscle function (Blow, 2015; Frignani, 2017; Zimiglia, 2014), but on the other hand, having a different elasticity from that of the tape, could reduce the range of motion (ROM) of the fingers (Frignani, 2017) and potentially could increase the risk of developing oedema in the control group.

Outcome evaluation details

OER nurses will evaluate the extent of oedema in the fracture-homolateral hand by measuring the circumference at the base of the 1st phalanx of the 1st finger and at the base of the 1st phalanx of the remaining 4 fingers merged together both at T0 and T1. The number of re-entries in OER between T0 and T1 will be registered. Furthermore, we will measure the intensity of pain with the Numerical Rating Scale (NRS) (Artioli et al., 2016; Peate et al., 2018) both at T0 and T1. At T0, the pain will be assessed before the possible administration of local anesthetic, while we do not expect differences between the intervention and the control group. Finally, the eventually analgesic use during the previous 4 hours will be recorded both at T0 and T1.

Procedure

An alphanumeric code will identify each patient in the case report form (CRF) and in the electronic database used for the analyzes, in order to guarantee pseudonymization.

We will report in the CRF the variables described in the Table 2.

Once the fracture reduction maneuver has been performed and the immobilization performed in a plaster cast, if the patient belongs to the intervention group, we will apply the tape only to the fingers of the hand with a lymphatic technique (Figure 2). We will not extend the application to the

metacarpals even if it would increase the surface of action, because portions of the tape will remain under the plaster, hiding possible skin reactions to the glue. Moreover, the tape application up to the metacarpals, inevitably performed before cast application, will increase the risk of detaching during the plaster wrap.

Blow (2015) suggests that the tape application needs to be proximal to the plaster cast. However, this indication is not supported by the literature. Other authors apply tape on the area that will probably form oedema (Donec, et al.,2014). Therefore, we believe that tape application on hand fingers is the most appropriate for achieving the objectives of this study.

The tape available at the Local Health Unit of Piacenza is the Leukotape K® by Essity, winner of the INTERCENTER AVEN tender for the supply of this type of medical device.

CRFs will be kept in OER until follow-up, so that any re-attendances can be noted.

Follow up

Even though tape results could be seen after 2-3 days, we choose to collect T1 variables (as previously described) at day 7 in order to avoid possible bias in the re-entry evaluation. The 7-day follow-up will be concomitant with the radiographic fracture control provided by organization procedure.

The completed CRFs will be delivered to the Researcher who will carry out the data analysis.

Statistical analysis

We will describe the general characteristics of the two groups. We will evaluate the effectiveness of randomization through the χ^2 test, for categorical variables, and the t-test, for continuous variables. Intervention group versus control group analyses will be performed by comparing the respective mean of: the T0-T1 differences of circumference of both thumb (*i*) and the other 4 fingers (*ii*), the pain NRS score at T1(*iii*), and the number of OER re-entries (*v*), by t-test for independent groups (after verifying the normality of the distributions with the Shapiro Wilk test).

All analyses will be performed on an Intention-To-Treat principles: all randomized patients will be analyzed in the arm they were allocated by randomization. Only screening failures and patients

who refuse before the treatment start would be excluded. In the event of tape detachment in the first 48 hours after T0 and/or impossibility to evaluate study endpoints, missing data will be substituted by multiple imputation.

We will perform all analyzes using 2-tailed tests and consider significant a p value <0.05. We will report all analyzes according to the international guidelines for RCTs (Boutron et al., 2017).

REFERENCES

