* Further exclusion criteria introduced following advices of Blow and Kumbrink although to date there are no absolute contraindications to the application of elastic tapes (Blow, 2015; Kumbrink et al., 2019).

Table 2: Variables of study CRF and study timepoints.

Variable name	Unit of measurement or possible categories	T0 (day1)	T1 (day7)
Subject code	N/A	X	
Gender	Male/Female	X	
Age	Years	X	
Heart disease	Presence/Absence	X	
Kidney pathologies	Presence/Absence	X	
Respiratory diseases	Presence/Absence	X	
Diabetes	Presence/Absence	X	
Hypertension	Presence/Absence	X	
Assigned group	0/1	X	
Fractured limb	Right/Left	X	
1 st finger circumference	Cm	X	X
Circumference of the remaining 4 fingers merged together	Cm	X	X
NRS	0-10	X	X
Analgesic use during the previous 4 hours	Yes/No	X	X
Accidental removal in the 48 hours after T0	Presence/Absence		X
Accidental removal	Presence/Absence		X
OER re-attendance between T0 and T1	Natural number		X

FIGURE LEGENDS

Figure 1. CONSORT flowchart modified for Randomized Trials of Nonpharmacologic Treatments (Boutron et al., 2017)

Figure 2. Tape application: a. lateral view, b. sight fly, c. dorsal view

FIGURES

[figure not shown]

Figure 1

Figure 2.

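### Analgesic use after baseline is recorded only for the 4 hours before the day-7 visit, and no between-group comparison of it is planned

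*Combined protocol and SAP*

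**What the plan says.** The Aim section states that "we aim to assess the differences in pain and cast tolerability between the intervention group and the control group". It names no period for the pain comparison. Under Secondary endpoints, pain is defined as "i) pain intensity at T0 and T1" and the analgesic endpoint as "ii) analgesic use during the previous 4 hours at T0 and T1".

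Outcome evaluation details confirms how the second is collected: "the eventually analgesic use during the previous 4 hours will be recorded both at T0 and T1". Table 2 carries the variable "Analgesic use during the previous 4 hours" as a Yes/No field, once at day 1 and once at day 7. No drug, dose, count or diary is listed.

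The Statistical analysis section gives the between-group comparisons in one sentence. It begins with the thumb (i) and four-finger (ii) circumference changes and ends with "the pain NRS score at T1(*iii*), and the number of OER re-entries (*v*), by t-test for independent groups". The numbering passes from (iii) to (v). The χ² test appears in that section only as a check on randomization.

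On timing, the Follow up section says: "Even though tape results could be seen after 2-3 days, we choose to collect T1 variables (as previously described) at day 7". It adds that the date was chosen to protect the counting of re-entries from bias and that it coincides with the routine radiographic check.

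**The concern.** Two gaps meet in the same endpoint.

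The first is in measurement. A patient who took analgesics every day but none in the 4 hours before the day-7 visit is recorded as No, exactly like a patient who took none all week. A difference between arms in use during the treated week could therefore go unseen.

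The second is in analysis. A declared secondary endpoint has no planned comparison, so any test reported later would be chosen after the fact. It also leaves the pain result hard to read. Similar NRS scores at T1 could mean similar pain, or similar pain reached with more medication in one arm. The plan does not look at the one item it collects that bears on this.

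**Working it through.** **1. The plan's own figure.** The sample size section uses d = 0.4, α = 0.05 and power 0.80; the Statistical analysis section specifies two-tailed tests. With the normal approximation, n = 2 × (1.960 + 0.842)² / 0.4² = 98.1, so 99 per arm. The exact t-test calculation gives 99.08, rounded up to the stated 100 per arm, with power 0.80. The figure reproduces. It concerns circumference and does not bear on the analgesic point, except that it supplies the 100 per arm used in step 4.

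**2. How much of the interval the item covers.** The look-back is 4 hours (Secondary endpoints, Table 2).
- T1 seven days after T0: 7 × 24 = 168 hours; 4/168 = 2.4%.
- Table 2's day 1 to day 7 read as six days: 6 × 24 = 144 hours; 4/144 = 2.8%.

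The T0 look-back lies before treatment and cannot show a tape effect.

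**3. Endpoints set against planned comparisons.**

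| Endpoint | Collected after T0 | Item in Statistical analysis |
|---|---|---|
| Thumb circumference change | T1 | (i) |
| Four-finger circumference change | T1 | (ii) |
| Pain NRS | T1 | (iii) |
| Analgesic use | T1, previous 4 hours | none |
| OER re-entries | whole T0–T1 interval | (v) |

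Two primary and three secondary endpoints make five. The analysis list runs to (v) but has four entries, and the empty slot is where analgesic use would fall. The only test named for the list is the t-test, which is not the natural choice for a Yes/No variable. No other section supplies the analysis.

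**4. Illustration only, on assumed rates.** The documents give no analgesic rates. Arcsine method, two-sided 0.05, 100 per arm: h = 2·arcsin√p₁ − 2·arcsin√p₂; power ≈ Φ(|h|·√(100/2) − 1.96).

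| Assumed rates | What they stand for | Power |
|---|---|---|
| 50% v 30% | any use since T0 | 0.83 |
| 15% v 9% | 30% of those users dosed in the last 4 hours | 0.26 |
| 10% v 6% | 20% of them | 0.18 |
| 5% v 3% | 10% of them | 0.11 |
| 95% v 90% | near-universal use since T0 | 0.27 |

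For the first row, h = 0.41 and Φ(0.41 × 7.07 − 1.96) = Φ(0.95) = 0.83. A since-T0 item can carry far more information than the 4-hour item, but the last row shows that a yes/no version may not. That is the reason for also asking the number of days.

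**The case against.** The strongest reply is that the stated pain aim is met. The protocol sets no first-week or cumulative pain objective; it defines pain intensity at T0 and T1, and "the pain NRS score at T1" is both collected and compared. A reader might infer that the trial cannot answer its pain question at all. The documents do not support that.

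A reader might also infer that the protocol expects pain relief at 2–3 days and then fails to measure it. The Follow up sentence speaks of tape results in general, does not mention pain and does not say that the effect ends then. The tape stays on until day 7, and reasons for the day-7 visit are given. Those reasons explain the visit date, however, and not a 4-hour look-back at that visit.

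The 4-hour item has a proper use: it shows whether the NRS was given under recent analgesia. This stands, and it is a reason to keep the item and to analyse it. OER re-entries do cover the whole interval, but they are an indirect measure and not specific to pain or analgesic use.

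The missing (iv) may be a drafting slip. That is plausible, and nothing in the documents shows that the endpoint was dropped on purpose. The plan as written still gives no analysis for it.

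**Conclusion.** The point holds in limited form. Secondary endpoint (ii) has no planned between-group analysis, and its post-baseline window is 2.4–2.8% of the T0–T1 interval. The trial therefore cannot compare analgesic use over the treated week, and the T1 NRS is compared without a planned look at analgesic use. Pain at day 7 can still be compared between arms.

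The coverage figures and the missing item come straight from the documents and need no assumption beyond how day 1 to day 7 is counted. The power figures rest wholly on assumed rates. They show why the window matters but are not estimates for this trial, and the plan claims no power for secondary endpoints. The primary endpoints are unaffected. This is a cheap improvement worth making.

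**What to change.** **Case report form.** At the existing T1 visit, add one question: any analgesic use since T0 (yes/no) and, if yes, on how many days. Keep the NRS and the 4-hour item as they are. Replacing the current-pain NRS with recalled worst pain is not recommended: in an open-label trial that would trade a current reading for one more open to recall and expectation.

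**Statistical analysis.** Restore item (iv), for example:

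> (iv) Analgesic use at T1, in the previous 4 hours and since T0, will be compared between groups as proportions, with the risk difference, its 95% confidence interval and a χ² or Fisher exact test. The number of days of use since T0 will be summarised by group. These results will be reported beside the T1 NRS comparison.

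**If the new question can no longer be added.** Restore item (iv) for the 4-hour item alone, and limit pain and analgesic conclusions to day 7.

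**Cost.** A small CRF amendment, one extra question at a visit that already takes place, and a short addition to the analysis section. One-week recall is less exact than a current reading. It is also open to expectation bias, because there is no sham tape and data collection is unblinded; the report should say so.

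### The analyst is promised to be blind, but receives CRFs that pair the 0/1 group code with removal fields only a taped patient can trigger

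*Combined protocol and SAP*

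**What the plan says.** - **Blinding.** The Design section describes a trial "with parallel design and blinded data processing". Under Randomization, blind and control: "The data-analyzing Researcher will not know which of the two groups will be the intervention nor the control one, to guarantee the blind". The same section concedes that the investigators cannot collect data blind, so masking of the analyst is the only masking claimed.
- **Control arm.** "We decided not to apply any type of alternative strip to the control group".
- **CRF content.** The Procedure section puts every Table 2 variable on the CRF. Table 2 lists the assigned group (0/1) and two Presence/Absence fields recorded at T1: accidental removal within 48 hours of T0, and accidental removal without a time limit.
- **Data flow.** Under Follow up: "The completed CRFs will be delivered to the Researcher who will carry out the data analysis". The Procedure section also says a pseudonymous code identifies each patient on the CRF and "in the electronic database used for the analyzes".
- **Missing data.** Under Statistical analysis, the intention-to-treat statement is that "all randomized patients will be analyzed in the arm they were allocated by randomization". Two sentences later comes the imputation rule. Its trigger is worded "In the event of tape detachment in the first 48 hours after T0 and/or impossibility to evaluate study endpoints". The remedy it prescribes is that "missing data will be substituted by multiple imputation".

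**The concern.** A 0/1 code masks the analyst only if nothing in the same record shows which code wears tape. The removal fields can show exactly that. A control has no tape to lose, so a single entry of Presence labels that patient's code as the intervention for every patient. Blanks or not-applicable marks confined to one arm would do the same without any removal.

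What is at stake is the choices still open when the data arrive. The core comparison is fixed: a two-tailed t-test on the T0–T1 differences. The imputation model is not specified, and neither is the action if the Shapiro-Wilk test rejects normality. An analyst who knows the taped code could settle either one with the direction of the result in view.

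The missing-data sentence adds to the problem because it can be read in two ways. If early detachment alone triggers imputation, the analyst needs the 48-hour field, and measured T1 values would be replaced in the taped arm only. That sits badly with the intention-to-treat statement. If only values that are actually missing are imputed, the analyst does not need the field and it can be withheld.

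**Working it through.** **Step 1: does any stated safeguard separate the group code from the removal fields?**

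| Safeguard in the plan | What it protects | Closes the route? |
|---|---|---|
| Group coded 0/1 | Meaning of the code, if nothing else reveals it | No; the removal fields are on the same CRF |
| Password on the randomization list | The list | No; the analyst does not need the list |
| Alphanumeric patient code | Patient identity | No; it does not mask the arm |
| Electronic database for the analyses | Not said to omit any field | No; the CRFs reach the analyst anyway |

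The Table 2 removal rows do not contain the word tape. That they concern tape is inferred from the missing-data sentence, which speaks of tape detachment over the same 48 hours, and from the absence of any strip in controls. The blind holds on this route only if every control is entered as Absence and no removal is recorded. The plan ensures neither.

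**Step 2: how likely is at least one recorded removal?**

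Inputs from Sample size calculation: 100 per arm required, 110 per arm enrolled. The 100 reproduces: effect size 0.4, two-sided α 0.05 and power 0.80 give 99.08 per arm by the t-test calculation, rounded up to 100. The removal risk p is not in the documents, so it is assumed over a range, with removals independent between patients.

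Formula for n taped patients: P(at least one) = 1 − (1 − p)^n. For example, with p = 0.01 and n = 100, 1 − 0.99^100 = 0.634.

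Simple randomization does not fix the arm sizes. With 200 patients followed, each is taped and has a removal with probability p/2, so P = 1 − (1 − p/2)^200.

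| Assumed p | n = 100 | n = 110 | 200 followed, random arm size |
|---|---|---|---|
| 0.5% | 39% | 42% | 39% |
| 1% | 63% | 67% | 63% |
| 2% | 87% | 89% | 87% |
| 5% | 99.4% | 99.6% | 99.4% |

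Break-even risks at n = 100: the chance reaches 50% at p = 1 − 0.5^(1/100) = 0.69%, and 95% at p = 1 − 0.05^(1/100) = 2.95%. Below 0.69% the blind more likely than not survives this route. Blanks confined to one arm are a second route that cannot be quantified.

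**Step 3: would withholding the fields still leak the arm through missing values?**

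Assume 110 per arm, 10% unassessable in both arms, and early detachment risk d. If measured values are discarded on detachment, missing counts are Bin(110, 0.10 + 0.90d) in the taped arm and Bin(110, 0.10) in controls. The chance that guessing the arm with more missing values is right equals P(taped more) + 0.5 × P(tie).

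| d | Values discarded | Measured values kept |
|---|---|---|
| 0.5% | 54% | 50% |
| 1% | 59% | 50% |
| 2% | 67% | 50% |
| 5% | 85% | 50% |

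The 50% follows directly from assuming equal loss. If loss were 12% against 10% it would be 68%, and at 13% against 10% it would be 76%, for someone who already knew which arm loses more. With 5% rather than 10% unassessable, the discarded column becomes 56%, 62%, 72% and 91%. The comparison shows only that keeping measured values prevents detachment itself from adding a hint.

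**The case against.** The strongest reply is that little bias can come from this. Circumference, pain score and re-entry counts are already recorded, by unblinded staff, before the analyst sees a CRF. The main test and significance level are fixed. The only path from unblinding to a shifted result is through the unspecified imputation model and normality fallback, and specifying those would remove nearly all the harm even if the removal fields stayed visible. The probabilities above measure the chance of unblinding, not of bias, and rest on assumed removal rates. An analyst may also guess the arm from the direction of the results.

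All of that stands, and it limits the importance of the point. It does not restore the guarantee. The protocol promises that the analyst will not know the arms, and its own data flow does not secure that.

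Two further objections bear on the repair. First, the missing-data wording speaks of missing data, which favours imputing only absent values. If the sponsor meant the 48-hour field to trigger imputation, the repair changes the primary analysis and is more than an export step. Second, the protocol says the Data Analysis Manager is not involved in clinical evaluation, but never says this person is distinct from the analyst. Both are fair, and the fix has to settle them explicitly.

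A masking step that exists in practice but is not written down cannot be excluded. In that case the remedy is to write it down.

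**Conclusion.** The concern holds. Followed as written, the plan leaves an unprotected route from the 0/1 code to the taped arm. Whether it opens depends on a removal rate the documents do not give: it is more likely than not above about 0.7% and near certain at 5%, assuming independent removals and 100 taped patients. This is an open route, not evidence that unblinding occurred.

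The effect on the result cannot be estimated from the documents. Sample size, power and α are unaffected, and open outcome measurement remains whatever is done here. The point should be corrected because the property at risk is the only masking claimed and the correction is cheap. Confidence is medium, since the practical consequence depends on analysis choices not yet specified.

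**What to change.** 1. **Follow up.** Replace delivery of the completed CRFs to the analyst with a 0/1-coded dataset prepared by the Data Analysis Manager. It should omit both removal fields and keep every measured T0 and T1 value. The revised text must state that the Data Analysis Manager and the analyst are different people.
2. **Statistical analysis.** Reconcile the missing-data sentence with the intention-to-treat statement, so that multiple imputation applies to endpoints that are actually missing and detachment alone does not discard a measured value. The analyst then does not need the removal fields for the primary analysis.
3. **Before release.** Fix in writing the imputation model and the action if the Shapiro-Wilk test rejects normality. This also limits the harm if the analyst guesses the arm from the results.
4. **After lock.** Release the removal fields, and run any analysis that uses them, once the primary results are locked.
5. **Otherwise.** If the data flow stays as it is, qualify the blinding statements under Design and under Randomization, blind and control.

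The cost is one extra export, a few sentences of protocol text and slightly later adherence summaries. It is higher if the sponsor intended early detachment to trigger imputation, because item 2 would then change the primary analysis, or if the Data Analysis Manager and the analyst are currently the same person.

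### Nothing in the plan keeps the T0 circumference from the unblinded nurse who takes the T1 reading, although both primary endpoints are the difference between the two

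*Combined protocol and SAP*

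**What the plan says.** The Procedure section sets the content of the form: "We will report in the CRF the variables described in the Table 2". Table 2, titled "Variables of study CRF and study timepoints", marks the arm once, at T0 ("Assigned group 0/1 X"). It marks both circumferences at T0 and again at T1 ("1 st finger circumference Cm X X" and "Circumference of the remaining 4 fingers merged together Cm X X"). It lists no field for the change itself.

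On handling, the Procedure section states: "CRFs will be kept in OER until follow-up, so that any re-attendances can be noted". The Follow up section adds: "The completed CRFs will be delivered to the Researcher who will carry out the data analysis". Under Outcome evaluation details, OER nurses take the circumferences at both times. Under Setting, the day-7 measurements and the tape removal take place at the orthopaedic outpatient clinic.

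On blinding, the section Randomization, blind and control says: "The Investigators are not allowed to collect data in a blind way due to the nature of study intervention". Only the analyst is kept unaware of which code is the intervention.

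The plan does not mention a separate T1 page, concealment of the T0 value, or a duplicate or independent T1 reading.

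**The concern.** A circumference taken by hand depends on how tightly the measuring tape is pulled and exactly where it sits, so the reader has some latitude. The T1 reading fixes the primary endpoint, because T0 is already known. With the T0 figure in view, one subtraction gives the patient's result.

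Two things follow. The reader may drift towards the earlier value, which makes changes look smaller than they are. And a reader who knows the arm also knows which side of T0 would count as success for it. Blinding the analyst cannot repair values that were recorded with bias.

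The plan gives a reason why the arm cannot be hidden from those who collect data. It gives none for leaving T0 unconcealed, and T0 can be concealed even when the arm cannot.

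**Working it through.** **1. The plan's own figure.** Inputs from Sample size calculation and Statistical analysis: effect size 0.4 SD, two-sided alpha 0.05, power 0.80, 1:1 allocation. The exact two-sample t-test needs 99.08 per arm, rounded up to 100, and power at 100 per arm is 0.804. Adding 10% gives 100 × 1.10 = 110 per arm, or 220 in total. The stated figures reproduce, and nothing below changes them.

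**2. What the passages establish together.**

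| Question | Where | Answer |
|---|---|---|
| Are T0 and T1 circumferences in the same CRF? | Procedure, Table 2 | Yes, as variables of one CRF |
| Is the form kept from T0 to T1? | Procedure | Yes, in OER |
| When does it go to the analyst? | Follow up | Once completed |
| Who reads T1? | Outcome evaluation details | OER nurses |
| Where is T1 read? | Setting | Outpatient clinic |
| Is the reader blind to arm? | Randomization, blind and control | No |
| Is T0 hidden at T1? | Nowhere | Not stated |
| Is the form in view during the reading? | Nowhere | Not stated |

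The natural reading is one form, opened at T0 and completed at T1, with no safeguard. Whether the reader looks at T0 before fixing T1 is left open.

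**3. Anchoring that is equal in both arms.** Let D be the true change, with arm means μ_T and μ_C and SD σ. Suppose the reader pulls T1 towards T0 by a fraction k, so the recorded change is D* = (1 − k)D. Then:

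- difference in means = (1 − k)(μ_T − μ_C)
- SD = (1 − k)σ
- t statistic: the factor (1 − k) cancels, so t is unchanged.

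The false-positive rate stays at 5%, but the estimated difference in cm is too small. The documents give no value for k. If k is assumed to be 0.1, 0.2 or 0.3, the estimate is 90%, 80% or 70% of the true difference. If part of the reading error is not shrunk in the same way, the SD falls by less than the difference does, and some power is lost as well.

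**4. Anchoring that differs by arm.** With no true effect and mean change μ in both arms, the recorded difference is (1 − k_T)μ − (1 − k_C)μ = (k_C − k_T)μ, or (k_C − k_T)μ/σ in SD units. The documents give none of k_T, k_C, μ or σ, so this cannot be evaluated.

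**5. A general arm-dependent reading bias, for scale only.** Assume a systematic difference b between arms, in SD units of the change, with 100 per arm and no true effect. The noncentrality is b√(100/2) = b√50, with 198 degrees of freedom.

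| b (SD, assumed) | b√50 | Chance of p < 0.05 |
|---|---|---|
| 0 | 0 | 5.0% |
| 0.05 | 0.35 | 6.4% |
| 0.10 | 0.71 | 10.8% |
| 0.20 | 1.41 | 29.1% |

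A bias of one quarter of the planned effect (0.4/4 = 0.10 SD) would about double the error rate for each primary endpoint. This bias needs knowledge of the arm, which the tape gives whatever the form shows. The table therefore describes unblinded measurement in general. It is not the effect of seeing T0, and hiding T0 does not remove it.

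**The case against.** The strongest reply is that Table 2 lists variables by timepoint and is not a page layout. Forms are kept in OER while T1 is read at the outpatient clinic, and the plan does not say when the form reaches the clinic or whether it is open during the reading. This stands. A reader might infer that the nurse sees the change score while measuring, but the documents do not say so and no change field is listed. They support only that nothing prevents sight of T0.

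A reader might also infer that the group code on the form unblinds the measurement. It adds almost nothing. There is no sham strip, the tape stays on the fingers until the day-7 visit, and the plan discloses unblinded collection.

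A third tempting step is to quote an inflated false-positive rate as the cost of this form. Step 3 of the working shows that equal proportional anchoring does not move that rate. The rates in step 5 come from a different mechanism.

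Finally, seeing the earlier value lets a nurse catch a gross slip on the spot. That benefit is real. It can be kept by making the comparison after the T1 reading has been entered.

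**Conclusion.** The point holds in a limited form. As written, one CRF per patient appears to carry T0 forward to the T1 visit, and no rule stops the unblinded reader from seeing it while taking the reading that determines both primary change scores. The likely consequences are an estimated difference that is too small and, for a reader who knows the arm, exact knowledge of which reading would favour it.

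The size cannot be estimated from the documents. The conclusion rests on reading the Procedure section, the Follow up section and Table 2 as describing a single form. If T1 is in fact recorded on a sheet without the T0 values, the sponsor need only say so.

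This is a cheap improvement to measurement. It does not show that the trial's result would be wrong.

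**What to change.** Record the two T1 circumferences on a separate sheet that carries only the subject code. Add to Outcome evaluation details and to Follow up:

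> T1 circumferences are measured and recorded without sight of the T0 values; the T0 page is joined, and the tape-removal and re-attendance fields completed, only after the T1 readings are entered.

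This order matters because Table 2 makes the two tape-removal fields and the re-attendance count T1 variables. They must still be completed at that visit, and detachment within 48 hours feeds the multiple-imputation rule in Statistical analysis.

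The cost is one reprinted page and one sentence, with no extra staff. The downside is that a gross slip cannot be checked against T0 until the reading is recorded. If a re-measurement is then made, record it beside the first T1 value and do not overwrite that value.

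The change does not blind the reader to arm, and neither the protocol nor the report should describe it as doing so.
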